1 INTRODUCTION

Chronic prostatitis (CP) is a disabling condition affecting an untold number of men of all ages and ethnic origins. As early as 1980, the National Ambulatory Care Survey reported 20 office visits/1,000 men/year for symptoms compatible with prostatitis(1). Although by one estimate, 50% of men will suffer from symptoms of prostatitis at some point in their lives, most symptomatic men do not have bacterial prostatitis, for which the treatment and management is usually successful(2). Therefore, as noted by Krieger *et al*(3), the most common syndromes for men with chronic prostatitis are *idiopathic* (abacterial prostatitis). Depending on the status of the expressed prostatic secretions (EPS), these patients with chronic abacterial prostatitis are classified further as a) nonbacterial prostatitis if the EPS is purulent (leukocyte count elevated) or b) prostatodynia if the EPS is not purulent. To date there is no standardized method of diagnosis and treatment of this condition. As noted recently by Nickel and Sorensen(4), the problems and frustrations found in clinical trials investigating therapies for nonbacterial prostatitis are that

"our definition of the syndromes is unclear, the etiology is obscure, the relevance of the only objective finding we have (leukocytosis) is unknown, symptoms are highly variable, the natural history of the disease has not been adequately studied and the numbers in most clinical trials, including ours, are small".

They concluded that "since the symptoms are paramount in these patients, evaluation of response can only be achieved by using reproducible and validated symptom evaluation instruments."

Recognizing the importance of addressing problems in the diagnosis and treatment of prostatitis, a National Institute of Diabetes, Digestive and Kidney (NIDDK) Diseases Workshop on Chronic Prostatitis(5) was held in Bethesda, MD on December 7-8, 1995, from which the new consensus working definition and classification of prostatitis syndromes (NIDDK reference standard) for research studies on these diseases and disorders was summarized as follows:

1. *Acute bacterial prostatitis* is an acute infection of the prostate.
2. *Chronic bacterial prostatitis* is a recurrent infection of the prostate.
3. *Chronic nonbacterial prostatitis/chronic pelvic pain syndrome* (CPPS), where there is no demonstrable infection. Subgroups of this class are:
 - 3a) *Inflammatory chronic pelvic pain syndrome*, where white cells are found in the semen, expressed prostatic secretions (EPS), or voided bladder urine-3 (VB-3).
 - 3b) *Non-inflammatory chronic pelvic pain syndrome*, where white cells are NOT found in the semen, EPS, and VB-3.
4. *Asymptomatic inflammatory prostatitis* (AIP), where there are no subjective symptoms but white blood cells are found in prostate secretions or in prostate tissue during an evaluation for other disorders.

Patients in Categories 1-3 are characterized by chronic pain; however, unlike patients in Category 1 & 2, patients with Category 3 prostatitis do not have any detectable infection of the prostate as determined by conventional microbiological techniques. Abnormalities in the EPS are the primary objective features of Category 3 prostatitis and chronic pain is the primary subjective symptom. The majority of patients with chronic prostatitis are Type 3(3).

[figure not shown]
The occurrence and persistence of pain as a primary presenting symptom is an important aspect of both diagnosis and outcome evaluation. In the recent review article in *Pain* by Egan and Krieger(6), they note that “chronic abacterial prostatitis is remarkably similar to chronic pain syndromes”, and accordingly they make the case for therapy based on multidisciplinary approaches to pain management, rather than the traditional ‘organ system’ approach. Many therapies have been tried for chronic prostatitis, with a primary focus on improving bladder outlet resistance. However, the general consensus among clinical urology research investigators conducting therapy trials involving chronic prostatitis patients is well reflected in the recent summary of Nickel and Sorensen(4) that

"more research and larger clinical studies in the nonbacterial chronic prostatitis syndromes are urgently required."

In response to these growing concerns about the diagnosis and treatment of Chronic Prostatitis, the NIDDK funded the Chronic Prostatitis Clinical Research Network (CPCRN), comprised originally of (6) Clinical Research Centers (CRCs) and a Data Coordinating Center (DCC), effective October 1, 1997. In preparation for this first clinical trial, four (4) additional clinical research centers have been added. The primary research questions being addressed by the CPCRN encompass the diagnosis, etiology, natural history and prognosis, and the development of treatment strategies focused on Chronic Abacterial Prostatitis - Chronic Pelvic Pain Syndrome (CPPS). In support of these broad research goals, the CPCRN developed a longitudinal Chronic Prostatitis Cohort (CPC) Study, to which patients are currently being accrued and followed. The group also coordinated the development and validation of a symptom severity index for CPPS. This index, known as the NIH-CPSI, will be used as a primary outcome measure for clinical trials in CP(7). In parallel with the CPC, a series of clinical trials designed to address specific treatment questions, both etiologic and palliative, will be conducted. This protocol represents the first multi-center randomized clinical trial (RCT) to be conducted by the CPCRN.

2 STUDY DESIGN

This CPCRN RCT will utilize a 2 x 2 factorial design with four arms to evaluate: 1) placebo + placebo, 2) placebo + tamsulosin hydrochloride (FLOMAX®) 3) placebo + ciprofloxacin (CIPRO®), and 4) tamsulosin hydrochloride (FLOMAX®) + ciprofloxacin (CIPRO®) as

displayed in Figure 1. All participants who meet eligibility criteria at baseline screening will be stratified by clinical center and randomized to one of the four treatment arms. The trial will last a total of 12 weeks. Participants will be treated for 6 weeks and followed for an additional 6 weeks. The primary objectives of this trial are:

1. To compare placebo, ciprofloxacin (CIPRO®), tamsulosin hydrochloride (FLOMAX®), and the combination of ciprofloxacin (CIPRO®) plus tamsulosin hydrochloride (FLOMAX®) with respect to efficacy endpoints in CP participants

including the NIH-CPSI, participant assessment of global improvement, and other laboratory and clinical outcome measures.

2. To evaluate the safety and tolerability of ciprofloxacin (CIPRO®), tamsulosin hydrochloride (FLOMAX®), and the combination in CP participants.

2.1 Study Time Frame

Approximately 184 participants, 46 per treatment arm, will be treated and followed for a total of twelve (12) weeks. The total time required for this trial will be approximately fourteen (14) months.

2.2 Study Organizations

The CPCRN consists of ten (10) clinical centers that will recruit participants for the RCT. All participants previously enrolled in the CPC will be offered RCT participation if trial eligibility criteria are met. Over 420 participants have been enrolled in the CPC as of March 31, 2001. The target accrual of participants is approximately 18-20 participants at each of the ten (10) clinical centers, resulting in 184 participants. It is expected that each clinical center will accrue participants at the rate of 2-3 participants per month, thus approximately ten (10) to twelve (12) months will be required for accrual. The ten (10) Clinical Centers that will enroll participants into the RCT are:

1. Brigham and Women's Hospital & Massachusetts General Hospital, Harvard University Medical School, Boston, MA 02115
2. Temple University Hospital, Temple University, Philadelphia, PA 19140
3. University of Maryland Medical System, University of Maryland School of Medicine, Baltimore, MD 21201
4. Northwestern University Medical School, Northwestern University, Chicago, IL 60611
5. Harbor - UCLA Medical Center, University of California at Los Angeles, Los Angeles, CA 90024
6. Kingston General Hospital, Queen's University, Kingston, Ontario, Canada K7L 2V7
7. University of Mississippi Medical Center, Jackson, MI, 39216
8. Cleveland Clinic Florida, Weston, FL 33331
9. MLK Drew Medical Center, Los Angeles, CA 90059
10. University of Arizona, Tucson, AZ 85721

2.3 Study Endpoints

2.3.1 *Primary Endpoint*

The primary endpoint to be used for efficacy evaluation is the overall NIH-CPSI (Appendix A) (scale of 0-43). The change in this score from baseline to six (6) weeks will be calculated for each participant and compared among treatment groups (see Section 10.3 for details of primary endpoint analysis).

2.3.2 Secondary Endpoints

A number of secondary outcome measures related to both specific symptoms and overall symptom scores will be used to supplement the analysis based on the primary endpoint. One secondary endpoint will be a participant-reported global response assessment (GRA) at six (6) weeks or withdrawal; whichever comes first, relative to overall baseline symptoms. Additional symptom-related outcome measures include the NIH-CPSI subscales and MOS SF-12.

Laboratory measures to be followed include WBC in EPS. While the true significance of WBC count in the EPS has yet to be established, it nevertheless is the primary marker of intraprostatic inflammation that can be obtained non-invasively. The exact cutoff point for deciding that inflammation is present is also controversial, with most authors relying on 10 WBC per hpf in a wet mount sample. While many investigators have pointed out the variability of WBC count in participants with CPPS over time,(8) fluctuations in the short term, such as for durations contemplated in this study, are less of a problem(9).

3 STUDY AGENTS

3.1 Ciprofloxacin (CIPRO®)

Despite the fact that most urologists do not perform bacteriologic localization studies(10), the most common therapy for chronic prostatitis is antibiotics(11) and the most common antibiotic in use is ciprofloxacin. The advantages of ciprofloxacin are 1) excellent penetration into the prostate(12), 2) broad spectrum coverage of typical uropathogens as well as chlamydia and 3) high rates of bacterial eradication in participants with chronic bacterial prostatitis(13;14). The most common justification for treating CP participants with antibiotics is the belief that many of these participants have an infection due to cryptic or difficult to culture microorganisms. Indeed, culture of prostatic biopsy tissue in men with negative prostate fluid culture often demonstrates bacteria(15) and bacterial DNA can be isolated from prostate fluid(16) or prostate tissue(17) in a significant proportion of men with culture negative prostatitis. Whether bacteria detected in this manner represent true infection or colonization that is unrelated to symptoms is an issue that has still not been settled.

An alternate explanation for the symptomatic improvement that some CPPS participants achieve with ciprofloxacin could be its direct anti-inflammatory effect. Men with CPPS have documented elevations of inflammatory cytokines such as IL-1, IL-8 and TNF in their prostate fluid(18) and semen(19) as well as elevations in markers of oxidative stress(20). Interestingly, quinolones such as ciprofloxacin have been shown to directly inhibit IL-1 and IL-8 expression from in vitro studies(21;22). Successful treatment with antibiotics also lowers the level of prostatic oxidative stress(20). **(See Appendix D).**

Considering the prevalence of antibiotics as a treatment agent for men with chronic prostatitis and potential mechanisms effect, the objective of this study is to determine a definitive answer to the question of whether this treatment should be considered a guideline for standard therapy for chronic prostatitis.

Studies of quinolones in men with CPPS suggest that if an impact on symptoms is seen, the effect is detected by four (4) weeks ([name], personal communication). Therefore we believe that six (6) weeks of therapy should be sufficient to detect an improvement.

3.2 Tamsulosin Hydrochloride (FLOMAX®)

Alpha-blockers are some of the principal treatments for lower urinary tract symptoms due to benign prostatic hyperplasia (BPH). Since some of the symptoms of chronic prostatitis / chronic pelvic pain syndrome are similar to those of BPH, it has been postulated that alpha-blockers may be useful in the treatment of these conditions. Rosette examined the use of the alpha-blocker alfuzosin in men with chronic pelvic pain syndrome(23). In a double blind, placebo-controlled trial, there was no statistically significant difference in reduction in symptoms between men treated with alfuzosin and with placebo. There was, however, a significant difference between treated men and controls in terms of maximal urine flow. Duzendorfer in a similar trial using phenoxybenzamine, however, did find statistically significant improvements in several pain outcomes at six (6) weeks in treated participants compared to controls(24). The treatment group complained of orthostatic changes, which are not unknown in the use of alpha-blockers, but more “uroselective” alpha-blockers now likely reduce these potential side effects. Other studies have also looked at alpha-blockers, principally phenoxybenzamine, and have shown symptomatic improvement in approximately 50% of participants.

Tamsulosin hydrochloride (FLOMAX®) is a newer alpha-adrenergic blocking agent, which has been used extensively for the treatment of BPH. It is a methoxybenzene sulfonamide with a chemical structure that differs from second generation alpha-blockers such as prazosin and alfuzosin, which are quinazoline derivatives. Since it is an alpha 1A selective antagonist, dose titration is not necessary. There is little effect on blood pressure, which improves its overall tolerability. In clinical trials in the treatment of BPH, efficacy as measured by improvement in voiding symptoms and peak flow rates has been reported as significant compared to placebo(25;26). First dose orthostatic effects were rare and there were no significant ECG effects. (See Appendix E).

3.3 Combination of Ciprofloxacin (CIPRO®) and Tamsulosin Hydrochloride (FLOMAX®)

The etiology and pathogenesis of pain and voiding dysfunction in men with CPPS are not known and are likely multi-factorial. For instance, chronic infection may lead to irritation of muscles at the bladder neck, which might persist even after eradication of the infection. Alternatively, recurrent infection may be caused by persistence of residual urine in men with dysfunctional voiding. The rationale for the combination of ciprofloxacin and tamsulosin hydrochloride therefore is to 1) attempt to maximize eradication of bacteria by improving bladder emptying, 2) improve both pain and voiding symptoms, regardless of etiology and 3) gain insight into the pathophysiology of CPPS by comparing pretreatment culture and voiding parameters with response to medications.

In a retrospective, nonrandomized study, the combination of alpha blockers and antibiotics were superior to antibiotics alone in men with chronic bacterial prostatitis(27). For men with nonbacterial prostatitis, alpha-blockers were superior to antibiotics for improving symptoms. The combination of agents was well tolerated with no unique side effects seen. Indeed, there is

no mechanistic reason to suppose that a fluoroquinolone such as ciprofloxacin would interact with a selective alpha-1 blocker such as tamsulosin hydrochloride.

With regard to the pathogenesis of symptoms, one hypothesis to be tested is whether participants with urinary symptoms plus pain are somehow different from those with pain alone. If participants with pain alone, without voiding symptoms, respond to tamsulosin hydrochloride in the same way those with voiding symptoms, then the beneficial actions may be centrally mediated. If only participants with voiding symptoms respond to tamsulosin hydrochloride, then the action may be either central or at the end organ level. Similarly, it will be important to correlate any response to ciprofloxacin (CIPRO®) with the presence of bacterial growth in the prostate or urine for micro-organisms, especially bacteria considered to be “non-pathogens” such as gram positive bacteria. If eradication of bacteria is associated with an improvement of symptoms, then a pathogenic role is suggested. If improvement is seen regardless of culture status, then a direct anti-inflammatory role of the antibiotic would be likely.

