6 TREATMENT PROCEDURES

Participants meeting all eligibility criteria will be randomized electronically to one of the four treatment arms. Each participant will receive a 6 (six)-week supply of tablets containing ciprofloxacin (CIPRO®) (or its matching placebo), and a 6 (six)-week supply of capsules containing tamsulosin hydrochloride (FLOMAX®) (or its matching placebo). The study medications will be provided in tamper evident sealed bottles, and will be labeled according to regulatory requirement per Code of Federal Regulations (CFR), Title 21, Part 312.6.

The Research Coordinator will provide explicit instructions to the participant at the time of randomization and dispensing of study drugs. The participant will be instructed that if at any time he should miss a daily dose, he should take the next dose at the usual time. The participant may not “double-up” a dose. The participant will be instructed to save the containers, even if they are empty, and return all study medications at each follow-up visit, to assist the study in compliance monitoring.

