7.2 Screening Visit #1

The first screening visit should occur no more than three (3) weeks and no less than one (1) week prior to randomization. During this screening visit, the forms and procedures listed below will be completed. If a participant fails to meet any of the study eligibility criteria, based on the data collected during this visit, he would not be required to complete the physical examination, urinalysis, or urine culture for the purposes of the study. (See **Appendix C**).

1. *Eligibility Criteria.*

Each participant will complete a preliminary screening form that checks whether he meets the initial inclusion/exclusion/deferral criteria. (These criteria will be verified at the second baseline visit.)

2. *Participant Contact Information.*

Participants will be asked to provide the clinical center with their address, phone number, primary care physician, and the name and address of two other contacts. This information will be stored at the CRC and available only to selected study personnel. Participants who have previously enrolled in the CPC will be asked only to update the previous information.

3. *Participant Medical History.*

Each participant will provide the research staff with his general medical history and specific genitourinary medical history. In particular, the participant will be asked to provide information regarding his disease and surgical histories.

4. *Participant Symptom Index.*

[figure not shown]
Each participant will provide the research staff with an assessment of his discomfort/pain by completing the full NIH-CPSI.

5. *Physical Examination.*

Each participant will undergo a focused physical examination. This examination will include an abdominal exam, external genital exam, rectal exam, prostate exam, and perineal exam. Participants enrolled in the CPC who have completed a physical examination within one (1) month of enrolling in the RCT, will not be asked to complete another physical examination.

6. *Urinalysis, Urine and EPS Specimens for Microscopy and Culture.*

Each participant will provide the research staff with three (3) urine specimens and an EPS (expressed prostatic secretion) specimen for analysis and culture. The urine specimen will be collected via the classic “four-glass test” (FGT) described in Meares and Stamey(28). The FGT will be attempted one time only at each of Screening Visit #1 and at the six (6) week clinic visit.

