1. NIH-CPSI
2. MOS-SF12
3. Follow-Up Symptoms
4. Follow-Up Contact
5. Adverse Events/Serious Adverse Events
6. Voiding Log
7. Medication Diary
8. Concomitant Medications
9. Treatment Stop Form

Clinic Laboratory Procedures and Physical Exam:

1. Four Glass Microscopy and Culture Test
2. Post Void Residual
3. Physical Examination
4. Semen Sample (collected only if participant has localized uropathogens at baseline. Participant will be scheduled 2-3 days following clinic visit for semen sample collection).

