The serum elimination half-life in subjects with normal renal function is approximately 4 hours. Approximately 40 to 50% of an orally administered dose is excreted in the urine as unchanged drug. After a 250-mg oral dose, urine concentrations of ciprofloxacin usually exceed 200 mg/mL during the first two hours and are approximately 30 mg/mL at 8 to 12 hours after dosing. The urinary excretion of ciprofloxacin is virtually complete within 24 hours after dosing. The renal clearance of ciprofloxacin, which is approximately 300 mL/minute, exceeds the normal glomerular filtration rate of 120 mL/minute. Thus, active tubular secretion would seem to play a significant role in its elimination. Co-administration of probenecid with ciprofloxacin results in about a 50% reduction in the ciprofloxacin renal and a 50% increase in its concentration in the systemic circulation. Although bile concentrations of ciprofloxacin are several fold higher than serum concentrations after oral dosing, only a small amount of the dose administered is recovered from the bile as unchanged drug. An additional 1 to 2% of the dose is recovered from the bile in the form of metabolites. Approximately 20 to 35% of an oral dose is recovered from the feces within 5 days after dosing. This may arise from either biliary clearance or transintestinal elimination. Four metabolites have been identified in human urine which together account for approximately 15% of an oral dose. The metabolites have antimicrobial activity, but are less active than unchanged ciprofloxacin.

With oral administration, a 500-mg dose, given as 10 mL of the 5% CIPRO® Suspension (containing 250-mg ciprofloxacin/5 mL) is bioequivalent to the 500-mg tablet. A 10 mL volume of the 5% CIPRO® Suspension (containing 250-mg ciprofloxacin/5mL) is bioequivalent to a 5 mL volume of the 10% CIPRO® Suspension (containing 500-mg ciprofloxacin/5mL).

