Semen Sample Procedure

Participant Test Schedule: (Screening Visit #2)
(Post Clinic Visit #4*)

1. Instruct participant to remain abstinent for a minimum of two days.
2. Collect specimen in a sterile urine cup.
3. Measure volume in mls.
4. Plate 100 μ L on sheep blood agar (5%) plate and 100 μ L on MacConkey agar. Culture at 37°C for 5 days. Record results at 48 hours and 5 days.
5. Allow sample to stand at room temperature for thirty minutes.
6. Centrifuge for five minutes.
7. Aliquot seminal plasma into 1.0 - 1.5 ml cryovials.

Peroxidase Staining Procedure:

Prepare Benzidine-Cyanosine stock solution:

1. Dissolve 62 mg Benzidine (Sigma cat. # B3383) in 24 ml Methanol using a 100ml-graduated cylinder.
(Have 200ml of deionized H₂O boiling in a beaker. Dip 100ml graduated cylinder into boiling water, 30 seconds at a time, until benzidine is dissolved)
2. Add 75 mg Cyanosine (Phloxine B, Sigma cat. #P2759).
3. Add 26 ml boiling deionized or triple distilled H₂O.
4. Filter using Whatman #4 paper filter.

5. Store in brown bottle (solution is light sensitive) at room temperature for no more than 1 year.

Immediately prior to counting sample, make Benzidine-Cyanosine working solution:

1. Combine 1 ml Benzidine-Cyanosine stock solution (swirl vigorously before using) and 4 ul 3% H₂O₂.
2. Mix semen and Benzidine-Cyanosine working solution in 1:1 ratio (typically 20 ul each).
3. Place 20 ul of combination on a hemacytometer or slide with cover slip.
4. Scan slide under microscope at low power to assure even distribution of cells.
5. Count number of WBC per 5 high power fields (400X) after 5 minutes. WBC will be stained (pink/red) brown. Round cells which are not WBC (immature spermatids) will not be stained brown. The background will be pink.

- * Only for participants with localizing uropathogens at baseline visit #2 will provide semen sample 2-3 days after clinic visit #4.

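### Week-6 four-glass cultures, taken as ciprofloxacin dosing ends, cannot separate suppressed growth from eradication, which weakens and biases the pathogenic-role inference in section 3.3

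*Protocol*

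**What the plan says.** Section 3.3 gives two readings of a ciprofloxacin response. The first is "If eradication of bacteria is associated with an improvement of symptoms, then a pathogenic role is suggested". The second is "If improvement is seen regardless of culture status, then a direct anti-inflammatory role of the antibiotic would be likely". The section also plans to gain insight by "comparing pretreatment culture and voiding parameters with response to medications".

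The specimen schedule is as follows.

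- **Dosing.** Section 6: "Each participant will receive a 6 (six)-week supply of tablets containing ciprofloxacin" (or placebo). Section 6.1.1 makes it 500 mg twice a day.
- **Four-glass cultures.** Section 7.2, item 6: "The FGT will be attempted one time only at each of Screening Visit #1 and at the six (6) week clinic visit". Appendix C agrees. No interval off drug is required before the week-6 specimen.
- **After week 6.** Section 7.7 makes weeks 9 and 12 telephone contacts, without specimens.
- **Semen.** At week 6 a sample is "collected only if participant has localized uropathogens at baseline" (section 7.6). Appendix F says these men "will provide semen sample 2-3 days after clinic visit #4".
- **Baseline.** Section 4.1.3 defers men who used antimicrobials in the past four weeks, so the baseline culture is off drug.

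**The concern.** Eradication means that organisms are gone. A culture taken at the end of dosing shows only that they did not grow while drug was in the tract, and possibly in the specimen. Baseline is off drug and week 6 is at the end of drug, so change in culture status mixes clearance with drug presence.

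Two errors follow. Among men on ciprofloxacin, persisting infections that read negative join the cleared group, which dilutes any link with symptoms and shrinks the culture-positive group. Across arms, a negative culture becomes partly a label for having been given ciprofloxacin. If the drug helps by the anti-inflammatory route that section 3.1 proposes, negative cultures and improvement will still go together when arms are pooled. Section 3.3 would then read that as evidence for bacteria.

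**Working it through.** The protocol gives no eradication rate, sample size or power for this question, so there is no stated figure to reproduce. Three checks were made.

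**1. Is drug likely to be present at week 6?** Inputs from Appendix D:

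- serum half-life about 4 h;
- urine about 30 per mL at 8 to 12 h after 250 mg (printed as mg/mL; read here as µg/mL, an assumption);
- active drug in prostatic secretions;
- MIC of 1 µg/mL or less for most strains of one list of organisms.

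The trial dose is 500 mg, so 60 µg/mL is also tried (proportionality assumed). Urine is assumed to decline with the serum half-life:

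C(t) = C(12) × 2^(−(t−12)/4)

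| Hours after last dose | From 30 µg/mL | From 60 µg/mL |
|---|---|---|
| 12 | 30 | 60 |
| 24 | 30/8 = 3.75 | 60/8 = 7.5 |
| 36 | 30/64 = 0.47 | 60/64 = 0.94 |
| 48 | 30/512 = 0.06 | 60/512 = 0.12 |

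Time to reach 1 µg/mL is 12 + 4 × log2(30) = 31.6 h, or 12 + 4 × log2(60) = 35.6 h. Anchoring the label value at 8 h instead of 12 h takes 4 h off each (27.6 and 31.6 h). A urine specimen given within a day of the last tablet would still hold drug above 1 µg/mL. The label adds: "The urinary excretion of ciprofloxacin is virtually complete within 24 hours after dosing". A semen sample 2 to 3 days later should thus be largely free of carry-over if dosing stopped at the visit. The label gives no decay figure for semen or EPS.

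**2. What does misclassification do among men on ciprofloxacin?** Let e be the share of baseline-positive treated men truly cleared, s the share of the remainder who read negative on drug, and D the true symptom difference between cleared and uncleared men. Men who read positive are taken as truly uncleared. Then:

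- share reading negative = e + (1 − e)s
- observed difference = D × e / (e + (1 − e)s)

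Assume e = 0.6 and D = 4 points. Power uses 40 culture-positive men (assumed), the protocol's SD of 6.76, two-sided 0.05 and a normal approximation.

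| s | Reading negative | Observed difference | Negative / positive men of 40 | Power |
|---|---|---|---|---|
| 0 | 60% | 4.0 | 24 / 16 | 0.45 |
| 0.5 | 80% | 4 × 0.6/0.8 = 3.0 | 32 / 8 | 0.20 |
| 0.9 | 96% | 4 × 0.6/0.96 = 2.5 | 38.4 / 1.6 | 0.07 |

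With s = 0.9 and e from 0.4 to 0.8, the observed difference runs from 1.7 to 3.3. With 20 men, power at the three values of s is 0.25, 0.12 and 0.05; with 60 men it is 0.61, 0.28 and 0.08. Only at s = 1 is there no comparison group.

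**3. What happens if arms are pooled?** Suppose ciprofloxacin improves symptoms by D through a purely non-bacterial route. Let p1 and p0 be the shares of baseline-positive men reading negative with and without ciprofloxacin, in equal groups. The apparent difference between culture-negative and culture-positive men is

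D × [ p1/(p1 + p0) − (1 − p1)/((1 − p1) + (1 − p0)) ].

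This is above zero whenever p1 exceeds p0. With D = 4 and p1 = 0.96 (the last row above), it runs from 0 when p0 = 0.96 up to 4 × (1 − 0.04/1.04) = 3.85 when p0 = 0. No bacterial effect is needed to produce it.

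**The case against.** **The aim is exploratory.** Eradication is not an endpoint in section 2.3 and has no analysis in section 10.3.2; section 3.3 offers a suggestion, not a test. This stands and limits the weight of the point. The Data Analysis and Monitoring Plan may define eradication, but it cannot supply a specimen that the schedule does not collect.

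**Section 3.3 has its own safeguard.** If the drug works without bacteria, men with no baseline growth should improve too. This stands for pretreatment status, which week-6 timing does not touch. It does not repair the first reading, which rests on change in culture.

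**Week 6 matches the primary endpoint.** Whether symptoms follow bacterial load is informative even under suppression. That supports keeping the test there, but not calling its result eradication.

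**A reader might infer that the comparison cannot work, or that almost every ciprofloxacin man will be scored as cleared.** The protocol does not support this:

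- It gives neither the prevalence of baseline growth nor an on-drug conversion rate.
- The MIC list used above is described as of unknown clinical significance, and the label calls many *E. faecalis* strains only moderately susceptible.
- Appendix F plates 100 µL of urine or 10 µL of EPS, so drug in the specimen is diluted in the agar, though suppression in the tract is not.
- Section 8.6 seeks full data on men who stop early, so some may be cultured off drug.

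**A reader might also infer that men with only non-pathogens are the group the eradication sentence singles out.** That emphasis sits in the sentence on presence of growth, which can be answered from the baseline culture. It remains true that men without localised uropathogens have no scheduled off-drug culture after treatment.

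**Conclusion.** The point holds in a limited form. As scheduled, week-6 urine and EPS cultures cannot tell suppression from eradication, and a negative result partly marks assignment to ciprofloxacin. The pathogenic-role inference is seriously weakened within the ciprofloxacin arms and biased towards a bacterial explanation if arms are pooled. It is not void: with 60% truly cleared, an assumed 4-point difference still shows as 2.5 to 3.0 when 90% to 50% of persisting infections read negative. Power was low even without misclassification (0.45 with 40 men), so the conceptual bias matters more than the lost precision.

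The schedule facts come directly from the protocol. The drug levels rest on the unit reading, dose proportionality and the serum half-life applied to urine; e, s, D and the number of culture-positive men are assumptions. The primary endpoint and response by pretreatment culture are unaffected. This is a cheap improvement, not a defect in the main design.

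**What to change.** 1. Keep the four-glass test at week 6 for everyone, and record the date and time of the last study tablet with the specimen.
2. In section 3.3 and wherever results are defined, call the week-6 culture result *on-treatment culture conversion (suppression or clearance not distinguished)*, and withdraw the pathogenic-role inference from it.
3. Reserve *eradication* for the existing semen culture 2 to 3 days after the visit. State that it covers only men with localised uropathogens and is too early to exclude relapse; the label's own sinusitis trials judged cure about 30 days after treatment.
4. Rest the mechanistic question on the randomised ciprofloxacin effect by pretreatment culture status, which section 3.3 already contemplates.

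Moving the four-glass test to the later appointment for men with baseline growth looks attractive but is a poor trade. White cell counts in EPS (section 2.3.2) and in the four-glass test (section 10.3.2) would be on treatment in some men and off treatment in others, split by baseline culture. It would add a visit with prostatic massage for some men and would still be too early to show relapse.

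The cost is wording plus one data item. The downside is a weaker exploratory claim about eradication.
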